## **5.7 Packaging**

Each tube of VALCHLOR contains 60g of a gel containing 0.016% w/w of mechlorethamine (equivalent to 0.02% mechlorethamine HCl) in a base of the following inactive ingredients: diethylene glycol monoethyl ether, propylene glycol, isopropyl alcohol, glycerin, lactic acid, hydroxypropylcellulose, sodium chloride, menthol, edetate disodium, butylated hydroxytoluene.

Study drug will be shipped to the Mayo Clinic research pharmacy in Florida and labeled upon receipt with statement "Caution: New Drug Limited by Federal law for investigational use."

## **5.8 Masking/Blinding of Study**

This is an open-label pilot investigation. Masking and blinding procedures are not applicable. Qualitative and quantitative evaluations of response to treatment will be recorded. Updated photographs will be included in participants' records at each visit.

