## 2 Study Objectives

The primary objective of this study is to assess the potential effectiveness of once daily application of Valchlor in decreasing disease activity in patients with Lichen Planopilaris. The primary measurement of efficacy will be with the Lichen Planopilaris Activity Index (LPPAI) before and after 6 months of treatment. Secondary measures of efficacy will be the mean follicular density, Physician Global assessment (PGA) score, and the Dermatology Quality of Life Index (DQLI) score before and after six months of therapy.

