### 3.5 Secondary Study Endpoints

The secondary outcome measures of efficacy at baseline and after 6 months of treatment will include:

- Mean follicular density as assessed using Canfield scalp photography
- Dermatology Quality of Life Index (DQLI) score : 10 standardized items measuring impact of skin disease rated as 0=not at all/not relevant; 1=a little; 2=a lot; 3=very much
- Physician Global Assessment (PGA) score : using standardized photography compared to the presenting baseline and scored as -1 = worse (no change to erythema with new areas of alopecia); 0 = no change; 1 = mild improvement (slight reduction in erythema, alopecia not progressive); 2= moderate (moderate reduction in erythema, alopecia not progressive); 3 = significant improvement (very mild erythema, alopecia not progressive); 4 = clear (no erythema, alopecia not progressive)

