## 6 Study Procedures

### 6.1 Visit 1 (Week 0/Baseline)

- a) Informed consent
- b) Review treatment protocol
- c) LPPAI baseline score
- d) PGA baseline score
- e) DLQI baseline score
- f) Review medical history and current medications
- g) Baseline photographs
- h) Assessments of hair density using phototrichograms
- i) Dispense 1 tube of study drug
- j) Urine Pregnancy Test (female patients of childbearing potential); start/confirm form of contraception

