### 6.3 Visit 4 (Week 24± 5 days)

- a) LPPAI score final
- b) PGA score final
- c) DLQI score final
- d) Review changes to medical history and current medications
- e) Screen/review adverse events
- f) Repeat photographs
- g) Assessments of hair density using phototrichograms
- h) Reconcile and collection of unused study drug
- i) Urine Pregnancy Test (female patients of childbearing potential); confirm form of contraception

Study Activity	Schedule of Events			
	Day 1 SCREENING BASELINE	Week 4 PHONE FOLLOW- UP	Week 12 FOLLOWUP	Week 24 FOLLOWUP
Visit Number	1	2	3	4
Allowable visit window in days		+/- 5	+/- 5	+/- 5
Review Eligibility	X			
Informed Consent	X			
Medical History	X			
Dispense/Reconcile Medications	X	X	X	X
Review Changes to Med History and Medications			X	X
LPPAI	X		X	X
PGA	X			X
DLQI	X			X
B-HCG (females)	X		X	X
Photographs/Hair Count	X		X	X
Review Valchlor Application Instructions	X		X	X
Screening for Adverse Events		X	X	X

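### The PGA, a secondary endpoint, is read from photographs with the baseline image identified; concealing image order is feasible and would reduce expectation bias at small cost

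*Combined protocol and SAP*

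**What the plan says.** - **Masking.** Section 5.8 calls the trial an open-label pilot and continues: "Masking and blinding procedures are not applicable". Section 8.4 says the same of unmasking.
- **How the PGA is read.** Section 3.5 defines it as a change score, "using standardized photography compared to the presenting baseline and scored as -1 = worse", running up to "4 = clear (no erythema, alopecia not progressive". There is one grade of worsening and there are four of improvement. Every improvement grade also requires that hair loss has not progressed.
- **Role.** The PGA is secondary. Section 2 states: "The primary measurement of efficacy will be with the Lichen Planopilaris Activity Index (LPPAI) before and after 6 months of treatment".
- **Images.** Section 6.1 lists "Baseline photographs" and section 6.3 (Week 24) lists "Repeat photographs". Images are also repeated at Week 12. Section 5.8 adds: "Updated photographs will be included in" the participants' records at each visit.
- **Reader.** The documents do not say who scores the PGA, whether that person treats the patients, or whether scoring takes place at the Week 24 visit (where section 6.3 lists it) or later. The data security text in section 9 mentions a Principal Investigator, Investigators and a Statistician.

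**The concern.** Open-label describes who knows the treatment. Whether the reader of a photograph knows which image came first is a separate choice, and section 5.8 closes it off without discussing it. The PGA grades rest on judgement (slight, moderate or very mild erythema), and a reader who knows which image follows six months of treatment may lean towards improvement.

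In a randomised trial part of that lean would cancel between arms. Here there is one arm and no placebo (sections 3.1 and 5.3), so all of it enters the estimate. Section 7.1 says the data are meant to give a preliminary efficacy estimate and to help design a larger study, so an inflated PGA result could be carried forward. The LPPAI needs reported symptoms and a pull test with the patient present. The PGA is the clinician-rated outcome that is already photographic and can be protected cheaply.

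**Working it through.** The plan states no figure for the PGA: section 7.1 gives no power calculation, effect size or SD. There is nothing to reproduce, and everything below except n = 20 and the scale limits is assumed.

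**1. Simple illustration.** Suppose knowing the order makes the reader one step optimistic in 5 of 20 patients.
- Shift in mean PGA: 5 × 1/20 = 0.25 points.
- Shift in proportion improved: at most 5/20 = 25 percentage points. This is reached only if all five move from 0 to 1. A patient moving from 2 to 3, or from -1 to 0, adds nothing to it.

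**2. What concealing order achieves.** Let b be the mean bias in points when order is known, and g the probability that a masked reader guesses the order correctly. On a symmetric scale a correct guess gives +b and a wrong guess gives -b, so

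residual bias = g·b - (1 - g)·b = b(2g - 1).

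This is 0 at g = 0.5, half of b at g = 0.75, and all of b at g = 1.

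**3. Chance of a spurious signal.** This is the probability that a 95% interval for the mean PGA excludes 0 when nothing has changed. It uses the normal approximation with n = 20 and standardised shift b(2g - 1)√20/SD. The two figures in each cell are for SD 1.5 and SD 1.0.

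| b (assumed) | Order known (g = 1) | g = 0.75 | g = 0.5 |
|---|---|---|---|
| 0.25 | 12% to 20% | 7% to 9% | 5% |
| 0.5 | 32% to 61% | 12% to 20% | 5% |
| 1.0 | 85% to 99% | 32% to 61% | 5% |

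For b = 0.5, SD = 1.0 and g = 1, the shift is 0.5 × √20 = 2.24, which gives 61%.

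**4. Whether the present scale can be used under masking.** Not unchanged, for two reasons.
- *Truncation.* If the images are shown in reverse, a true improvement of 2, 3 or 4 can be recorded only as -1, which decodes to 1. Averaged over the two orders, these improvements become (2 + 1)/2 = 1.5, (3 + 1)/2 = 2.0 and (4 + 1)/2 = 2.5.
- *Tilt.* Suppose nothing has changed and the reader prefers either image equally often, by 1 or 2 steps equally often. Collapsing every preference for baseline to -1 gives a mean of 0.5 × 1.5 + 0.5 × (-1) = +0.25, as large as the bias in step 1. Keeping the size on both sides gives 0.5 × 1.5 - 0.5 × 1.5 = 0. The plan's own scale has this asymmetry already.

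**5. Wording.** The PGA grades speak of new or progressing hair loss. These are statements about time order, which a masked reader cannot apply directly.

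**The case against.** The strongest case against is that unmasked assessment in an exploratory single-arm pilot is openly declared, and that little depends on the PGA. It is one of three secondary measures. No threshold, test or decision rule uses it. The response categories and the comparison with published treatments rest on the LPPAI (sections 3.4 and 7.2). Follicular density, for which section 3.7 names digital image analysis, already gives a less reader-dependent image outcome. All of this is correct and keeps the point small. Follicular density does not measure erythema, however, so it does not replace a protected PGA reading.

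Three practical objections also stand, and they limit what can be claimed.
- A reader might infer that order masking would remove expectation bias. The documents do not support that. This is a single site with 20 patients, so an existing investigator may recognise them. Section 1.1 says that progression causes irreversible hair loss, so new alopecia can show which image is later.
- A reader might infer that no extra staff are needed. That is plausible but not shown: neither the number of investigators nor their involvement in care is stated, and someone must code the images and hold the key.
- The -1 to 4 scale and its time-ordered wording do not suit masked reading, as steps 4 and 5 show. This calls for a different reading form; it does not defeat the idea.

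**Conclusion.** The point holds as a cheap improvement to one secondary endpoint. The PGA as defined requires the reader to know the baseline image, no concealed reading is planned, and the statement in section 5.8 does not follow from open-label treatment where an endpoint is read from stored photographs. Concealing order would reduce expectation bias. How far depends on how often the reader can tell the order: half the bias remains at an assumed 75% correct guess rate.

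The 0.25 points and 25 percentage points rest on an assumed bias in 5 of 20 patients, and the second figure is an upper bound. The values of b, g and SD in the table are also assumed. None of these figures is evidence that PGA results in this trial would be inflated by that amount. Nor do the documents support the wider inference that the main efficacy result is affected by this point or rescued by the fix: the LPPAI is assessed unmasked either way.

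**What to change.** Amend sections 5.8 and 3.5 to say that treatment is open-label but the Week 24 PGA is read with image order concealed:

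1. Strip visit labels from the baseline and Week 24 images and present each pair in random order, in one batch at study end, to an existing investigator, preferably one not treating the patient if available. State who reads and when.
2. Have the reader grade erythema and extent of alopecia in each image, or the A-versus-B difference on a symmetric scale, in order-neutral terms.
3. Have the statistician hold the key, decode the order and derive the PGA category by a rule fixed in advance. The rule must cover pairs with less erythema but more alopecia, which the present grades do not place.
4. Report the symmetric difference beside the PGA category, so that worsening is not truncated at -1.
5. State that masking is partial and that the LPPAI is assessed unmasked.

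In the same amendment, reconcile section 6.1, which schedules a baseline PGA score, with section 3.5, which defines the PGA as change from baseline.

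The cost is coding about 20 pairs, a revised reading form, and scoring later than the Week 24 visit. No visits or images are added.

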## **5.9 Receiving, Storage, Dispensing and Return**

### **5.9.1 Receipt of Drug Supplies**

The drug will be shipped by Actelion Pharmaceuticals US, Inc to the Mayo Clinic research pharmacy in Florida. Upon receipt of the of the study drug, an inventory will be performed and a drug receipt log filled out by the person accepting the shipment. Designated study staff will count and verify that the shipment contains all the items noted in the shipping invoice. Any discrepancies, damaged or unusable study drug in a given shipment will be documented in the study files. The sponsor-investigator must be notified immediately of any discrepancies, damaged or unusable products that are received.

### **5.9.2 Storage**

Prior to dispensing, Valchlor will be stored in the freezer at -13°F to 5°F (-25°C to -15°C). After dispensing, patients will be advised to store Valchlor in a refrigerator at 36°F - 46°F (2°C - 8°C). Patients should consult a pharmacist prior to using Valchlor that has been left at room temperature for longer than one hour per day.

### **5.9.3 Dispensing of Study Drug**

Regular study drug reconciliation will be performed to document drug assigned, drug dispensed, drug returns, and drug remaining. This reconciliation will be logged on the drug reconciliation form, and signed and dated by the study team. Drug dispensation will occur at scheduled follow-up visits.

#### **5.9.4 Return or Destruction of Study Drug**

At the completion of the study, there will be a final reconciliation of drug shipped, drug dispensed, drug returns, and drug remaining. This reconciliation will be logged on the drug reconciliation form, signed and dated. Any discrepancies noted will be documented and investigated, prior to return or destruction of unused study drug. Remaining drug will be destroyed on site will be documented in the study files. Participants will be required to return any unused study drug at the end of the study period.

## 6 Study Procedures

### 6.1 Visit 1 (Week 0/Baseline)

- a) Informed consent
- b) Review treatment protocol
- c) LPPAI baseline score
- d) PGA baseline score
- e) DLQI baseline score
- f) Review medical history and current medications
- g) Baseline photographs
- h) Assessments of hair density using phototrichograms
- i) Dispense 1 tube of study drug
- j) Urine Pregnancy Test (female patients of childbearing potential); start/confirm form of contraception

### 6.2 Visit 2 (Week 4 Phone Follow-up)

- a) Phone follow-up visit to assess any adverse reactions (if any)
- b) Dispense 2 tubes of study drug

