#### **1.6 Risks and Benefits**

The postulated benefits of Valchlor include immunomodulatory effects to induce clinical remission through local effects on lymphocyte proliferation and Langerhans cell function. These benefits will occur without the toxicities associated with systemic immunosuppression, and without the dose-limiting effect of epidermal and dermal atrophy seen with daily high potency topical corticosteroid use.

The possible risks associated with Valchlor include:

1. Flammable Gel. The gel formulation is an alcohol-based product and is flammable when exposed to fire or other flame before completely drying. This risk will be minimized through application instruction procedures provided to study participants and the exclusion of smokers in the study.
2. Embryo-fetal Toxicity. Toxicity has been demonstrated with systemic administration of mechlorethamine, the active ingredient of Valchlor gel. This risk is minimized in that topical application of Valchlor is not associated with detectable levels systemic absorption. Additionally, pregnant, nursing females, or females planning or actively trying to become pregnant will be excluded from the study. All female study participants of child bearing potential prior will be screened for pregnancy with urine B-HCG testing at all study visits and will be required to use one form of contraception during the study period.
3. Non-Melanoma Skin Cancer. Retrospective analysis has shown that 2% (3/128) of patients receiving Valchlor for the treatment of early stage MF developed non-melanoma skin cancer after one year of use. Many of these patients had previously received other treatments known to increase skin cancer risk, and thus the absolute risk directly attributable to Valchlor has not been established. This risk will be minimized in this study in that patients will have surveillance skin

screening at each follow-up visits, a shorter 6 month treatment interval, and once daily application versus the BID to TID application utilized in patients with MF.

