## 4.4 Early Withdrawal of Subjects

### 4.4.1 When and How to Withdraw Subjects

Patients are free to withdraw at any time and for whatever reason. No data will be collected for withdrawn subjects and withdrawn subjects may be replaced within the accrual period. There will be no follow-up for withdrawn subjects. Pre-specified reasons for discontinuing include, but are not limited to, the following:

- Patient Request: Patient decided that he/she did not want to continue (for any reason)
- Adverse Event: Patient experienced a related or unrelated event that would interfere with the study objectives/evaluation
- Lost to Follow-up: Patient did not come in for a visit and could not be reached by phone
- Treatment Failure: If in the Principal Investigator and/or Investigators' judgment, the patient's condition required another form of treatment
- Mechlorethamine sensitization: Patient develops contact dermatitis to Valchlor that cannot be managed with low potency topical corticosteroids
- Inclusion/Exclusion Discrepancy/Violation: Patient should not have been enrolled
- Noncompliance: Patient is not complying with the protocol requirements (i.e. visit schedule, dosing, regimen, etc.); a patient is to be withdrawn if he/she misses two consecutive visits
- Other: Any other reason

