## **5.2 Treatment Regimen**

All study participants will apply Valchlor 0.016% gel to involved areas at night, beginning with three times a week, (Mondays, Wednesdays and Fridays) and increasing to daily application after one month, if well tolerated, for a total of 6 months. Patients will be instructed to first part the hair away from involved area as needed, limit application to areas with alopecia and erythema, apply 30 minutes after showering or washing, and allow treated areas to dry for 5 to 10 minutes before covering with clothing or going to bed. Participants will be instructed to wash their hands with soap and water after applying Valchlor. Caregivers who assist in application will be instructed to wear disposable nitrile gloves when applying Valchlor and dispose with the household trash. Patients will be instructed to store Valchlor in the refrigerator away from foods at 36-46 degrees F and apply within 30 minutes after removing from refrigeration.

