## **5.4 Preparation and Administration of Study Drug**

The study drug will be stored and dispensed to patients at each study visit from the Mayo Clinic Florida Research Pharmacy.

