## **5.5 Subject Compliance Monitoring**

Study participants will be dispensed one 60 gram tube at the qualifying baseline exam, 2 tubes at week 4 following phone visit, and 3 tubes at the week 12 follow-up visit. They will be instructed to use one tube per 30 days and be will instructed to bring these tubes for all follow-up visits. Weights of each tube after 30 days of use will be recorded.

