### 6.2 Visit 3 (Week 12± 5 days)

- a) LPPAI score
- b) Review changes to medical history and current medications
- c) Screen/Review adverse events
- d) Repeat photographs
- e) Assessments of hair density using phototrichograms
- f) Dispense 3 tubes and reconcile study drug
- g) Review compliance
- h) Urine Pregnancy Test (female patients of childbearing potential); confirm form of contraception

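### Section 1.6 can be read as promising a pregnancy test at every visit, yet the Week 4 phone visit releases two of the six tubes with neither a test nor a contraception check

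*Combined protocol and SAP*

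**What the plan says.** Section 1.6, under embryo-fetal toxicity, says that participants of childbearing potential "will be screened for pregnancy with urine B-HCG testing at all study visits" and must use contraception during the study.

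Section 6 defines four numbered visits. Visit 3 lists "Urine Pregnancy Test (female patients of childbearing potential); confirm form of contraception", Visit 4 lists the same item, and Visit 1 lists the test with starting or confirming contraception. Visit 2, the Week 4 phone follow-up, has two items: a call about adverse reactions and "Dispense 2 tubes of study drug". Section 5.5 places this release as "2 tubes at week 4 following phone visit". In the Schedule of Events the dispensing row is marked at Week 4. The pregnancy-test row and the row for changes in history and medication are both blank there.

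Section 5.2 has dosing start at three nights a week, "increasing to daily application after one month, if well tolerated". The Week 4 tubes therefore go out at about the time of the step-up.

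**The concern.** If the phone contact counts as a study visit, a site that follows Section 6 exactly does not deliver the safeguard stated in Section 1.6. If it does not count, Week 4 is still the one point at which drug leaves the pharmacy without anyone being scheduled to ask about contraception or possible pregnancy.

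A participant who conceives soon after baseline has no scheduled test until about Week 12. Before then she receives the tubes that cover most of the interval. Nothing else planned for Week 4 is certain to pick this up. The directed adverse-event questions in Section 8.1 concern contact dermatitis and accidental mucosal or eye exposure, and open questioning would help only if she raised the matter herself.

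**Working it through.** There is no figure in the plan to reproduce. The check sets Section 1.6 beside the visit lists, then counts tubes and days.

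Inputs are the visit lists in Section 6, the Schedule of Events (windows of 5 days either way) and the tube counts in Section 5.5. Baseline is taken as day 0.

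| Contact | Day (window) | Tubes released | Urine test | Contraception check |
|---|---|---|---|---|
| Visit 1, baseline | 0 | 1 | yes | yes |
| Visit 2, Week 4 phone | 28 (23–33) | 2 | no | no |
| Visit 3, Week 12 | 84 (79–89) | 3 | yes | yes |
| Visit 4, Week 24 | 168 (163–173) | 0 | yes | yes |

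1. **Tests.** They fall at 3 of 4 numbered visits. The visit lists and the Schedule agree, so the blank at Week 4 is not an extraction fault.
2. **Releases.** Drug is released at Visits 1, 2 and 3, and 1 of these 3 has no check.
3. **Tubes.** 1 + 2 + 3 = 6. The Week 4 share is 2/6 = 33% overall, and 2/(1 + 2) = 67% of what is supplied before Week 12.
4. **Time covered.** At one tube per 30 days (Section 5.5), the baseline tube lasts to about day 30. The Week 4 tubes then cover about 84 − 30 = 54 of the 84 days to the next test, or 64%.
5. **Test intervals.** Baseline to Week 12 is 84 days (79–89). Week 12 to Week 24 is 168 − 84 = 84 days, with a shortest value of 163 − 89 = 74 and a longest of 173 − 79 = 94.
6. **After the fix.** A check would take place at about day 28 (23–33). Because a test would follow only if indicated, both scheduled test intervals stay as in step 5.

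The number of participants of childbearing potential is not given. The enrolment target of 20 is an upper bound only, and no count of affected participants is offered.

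**The case against.** The strongest reply is that Section 1.6 means clinic visits. Three things support it. The same section promises skin screening at each follow-up visit, which cannot be done by phone. The table of contents lists only three visits, at Weeks 0, 12 and 24, and on that list the promise matches the test schedule exactly. Section 5.8 has updated photographs in participants' "records at each visit", yet none are scheduled at Week 4.

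Against this, Section 6 numbers the call as Visit 2 and describes it as a visit, and the Schedule gives it a window. Section 5.4 has drug "dispensed to patients at each study visit", which would take in Week 4, although that sentence is not literal either, since Visit 4 dispenses nothing. The clinic-only reading is therefore plausible but not settled. A reader might infer that the protocol contradicts itself or that sites will breach it. The documents do not support that, because the operational sections agree with one another and only the wording of Section 1.6 is open.

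A second reply is that nothing requires a check at every drug release, and that 84 days is simply the chosen testing frequency, repeated from Week 12 to Week 24. This stands. On the clinic-only reading no commitment is broken, and the Week 4 question is an improvement rather than a correction.

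A third reply is that few participants may be concerned. Men are eligible, and Section 1.1 says the disease is seen mostly in women aged 45 to 70. This also stands, and it limits the size of the point.

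A reader might also infer that a participant who tested positive would stay on drug, because Section 4.4.1 does not name pregnancy. The documents do not support that either. The list is introduced by "Pre-specified reasons for discontinuing include, but are not limited to, the following" and ends with a catch-all item, pregnancy is an exclusion criterion, and the consent pages, where such instructions could stand, are not in the supplied text.

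**Conclusion.** The point holds as a minor one: an ambiguity in Section 1.6 about which visits carry a pregnancy test, and one drug release of three (2 of 6 tubes) with no test or contraception check. The missing check is certain from Section 6 and the Schedule. Whether it departs from Section 1.6 depends on what that section means by a study visit, which the text does not settle.

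Expected harm is low. Section 5.1 reports no detectable plasma mechlorethamine at 0.016% and no measurable drug or half-mustard at 0.032%. Baseline testing, required contraception and the exclusion of women planning pregnancy all remain. No efficacy or safety endpoint is affected.

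The day counts assume that the tubes go out on the day of the call; Section 5.5 says only that release follows it. The coverage figure assumes use at the instructed rate of one tube per 30 days.

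**What to change.** Make two text changes.

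- In Section 6.2 (Visit 2), before the dispensing item, add: *confirm form of contraception and ask about a missed period (participants of childbearing potential); urine B-HCG before release only if indicated*. Add a matching Week 4 entry to the Schedule of Events.
- In Section 1.6, state the testing schedule as *at all clinic visits (baseline, Week 12, Week 24)*.

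The cost is one extra question on a call that is already planned, an occasional indicated urine test, and a possible short delay in releasing tubes to the participant concerned. No routine test is added.
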